7.8 Risk-to-Benefit Rationale

Subjects who are bothered by utilizing a urinary catheter for bladder drainage and who are not candidates for prostatic treatments are offered a temporary alternative to their urinary catheter. Data from prior studies indicates that a high percentage of subjects who meet the inclusion criteria benefit from the procedure. For the majority of the subjects the benefit of the procedure outweighs the risks.

8 OBJECTIVES AND HYPOTHESES OF THE CLINICAL INVESTIGATION

8.1 Primary Objective

The primary objective of the clinical study is:

- To determine the proportion of subjects who achieve adequate bladder drainage over 90 days, defined as a post-void residual (PVR) of ≤ 150 ml.
- The pre-specified success criterion for this study is that ≥ 50 percent of subjects will achieve adequate bladder drainage over 90 days.

8.2 Secondary Objectives

The secondary objectives of the clinical study are:

- To measure the effects of the Spanner stent on bladder drainage, defined by:
- The proportion of subjects who achieve a post-void residual (PVR) of ≤ 150 ml over 30 days.
- The proportion of subjects who achieve a post-void residual (PVR) of ≤ 250 ml over 30 days.
- The proportion of subjects who achieve a post-void residual (PVR) of ≤ 250 ml over 90 days.
- To measure the effects of the Spanner stent over time on maximum flow rate (Qmax in ml/sec) as assessed by Uroflow
- To measure the effects of the Spanner stent over time on the International Prostate Symptom Score (IPSS)

CONFIDENTIAL

8.3 Study Hypotheses

8.3.1 Primary Endpoint: Assessment of PVR over 90 days

PVR levels will be monitored throughout the 90 days of stent use to confirm that the subject is able to successfully empty his bladder. PVR levels are assessed on Visits 1, 2, 3 and 4 while stent is in place using abdominal ultrasound. The hypothesis is that over 90 days of stent use, 50% of the subjects will be able to successfully empty their bladder, as defined by PVR of ≤ 150 ml at all four visits.

8.3.2 Secondary Endpoints: Other Assessments of PVR

The monitored PVR levels at Visits 1, 2, 3, and 4 will be further assessed as follows:

- The proportion of subjects over 30 days (Visits 1 and 2) with PVR ≤ 150 ml.
- The proportion of subjects over 30 days (Visits 1 and 2) with PVR ≤ 250 ml.
- The proportion of subjects over 90 days (Visits 1-4) with PVR ≤ 250 ml.

8.4 Adverse Events

Any Adverse Events (AEs), Serious Adverse Events (SAEs) and Unanticipated Adverse Device Effects (UADEs), to be documented from time of enrollment until the last study visit.

8.4.1 Exploratory Endpoints

- Qmax scores.
- IPSS scores.

9 DESIGN OF THE CLINICAL INVESTIGATION

The proposed investigation will be a prospective, multicenter, single-arm, open-label trial.

The study will be conducted at three to ten study centers in the US. Subjects will be enrolled in the trial for a period of up to 125 days, which includes up to 20 days of post-removal follow-up prior to study discharge. The objectives of the statistical analyses are to:

- Assess the effectiveness of the device in emptying of the bladder
- Assess the safety of the device in the population under study

The study will enroll approximately 105 subjects who are dependent on a urinary catheter and meet eligibility criteria. The study will consist of a 90 day treatment period. Subjects will be fitted with a Spanner stent and the stent will be replaced at an interval of approximately 30 days (25-35 days permitted) for a total of up to 90 days of use (75-105 days permitted). Subjects will complete the study upon removal of the Spanner stent after 90 days and one follow-up telephone call post-removal.

All participants will undergo approximately 90 days of Spanner use, in the form of consecutive Spanner placements each lasting approximately 30 days (25-35 days permitted). During the 90 days, data will be collected with respect to PVR, uroflow,

CONFIDENTIAL

urinary symptoms, subject satisfaction and the occurrence of adverse events. Cystoscopy will be performed prior to the initial stent placement and after the final stent removal to determine any effects of The Spanner on lower urinary tract anatomy.

9.1 Measures to Avoid Bias

- The investigators are independent from the sponsor and are experienced with similar procedures.
- The study uses standardized measurements for endpoints.
- The disposition of all screened subjects will be recorded.
- Analyses to address primary and secondary objectives will be performed using an intention-to-treat sample including all enrolled subjects who underwent an attempted Spanner device implant procedure.
- The study will be monitored by independent individuals qualified by education and experience.

9.2 Primary and Secondary Endpoints

Primary and secondary endpoints have already been described in CIP Section 8.

9.3 Methods and Timing for Assessing, Recording, and Analyzing Variables

Timing of testing and events is provided in Section 12.1 Study Activities Table. Data assessment and analysis is described in Section 14. Statistical Considerations.

Guidance for the categorization of adverse events is provided in Section 21.6 Managing Adverse Events. Recording guidance is provided in Section 15.1 Electronic Case Report Form Completion. The requirements for conducting and reporting uroflow are defined in **Attachment B**.

9.3.1 Requirements for Diagnostic and Laboratory Tests

9.3.1.1 Urinalysis (UA), Urine Culture and Sensitivity (UC&S) and Serum Creatinine

- Test Laboratory

Testing must be completed by an accredited laboratory. Documentation of accreditation of the laboratory must be provided to the study Sponsor prior to study initiation. A copy of the laboratory normal ranges must also be supplied to the Sponsor.

- Specimen Collection, Handling & Analysis Requirements
- Clean catch, voided, mid-stream urine samples of adequate volume (50 ml minimum) should be collected in sterile containers and forwarded promptly to the testing lab. If clean catch is not practical due to urinary retention, use a straight catheter to directly drain the bladder.
- Urinalysis with microscopy – A complete microscopic examination is required in addition to the routine urinalysis. Specifically, counts of white cells (WBC), red cells (RBC) and bacteria present in the sample are required.
- Urine culture – Required when Urinalysis suggests microbial infection. For positive urine cultures, the organism identification as well as the colony count must be provided.

CONFIDENTIAL

- Serum Creatinine- A serum creatinine blood test is required to monitor renal function throughout the study.

9.3.1.2 Post Void Residual Urine (PVR) Testing

PVR will be determined using abdominal ultrasound:

- Subjects with a minimum PVR > 350 ml will be prematurely removed from the study (see Section 21.5.8).
- Subjects with a minimum PVR greater than 250 ml (and less than 350 ml) will be scheduled for a follow-up visit within one week to monitor PVR.

9.4 Randomization

The study design is a non-randomized single-arm design.

9.5 Pooling of Study Centers

All statistical analyses will be conducted using overall analyses pooled across all study centers.

9.6 Equipment Maintenance and Calibration

During the site initiation and training visit SRS will assure maintenance and calibration of the equipment relevant for the assessment of the clinical investigation is performed and documented.

9.7 Procedures for Replacement of Subjects

Enrolled subjects will not be replaced.

10 EXPOSURE TO INVESTIGATIONAL DEVICES AND MEDICATIONS

10.1 Exposure to the Investigational Device

Subjects will use The Spanner for approximately 90 days, in the form of three consecutive Spanner placements each lasting approximately 30 days. The current US labeling of The Spanner does not anticipate the replacement of the initial stent after 30 days.

This is a single-armed clinical study so the study subjects will not be exposed to comparators.

10.2 Recommended Medications

10.2.1 Use of Urinary Tract Medications

Urinary tract medications may be continued, discontinued or initiated during the study period. Record the use of these medications on the eCRF system. Note that the use of certain urinary tract medications (anticholinergics and BPH medications) are prohibited from use during the study.

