14.3 Primary Effectiveness Variable and Pass/Fail Criteria

The primary effectiveness endpoint is the success/failure of the subject to have a successful urinary void at all four study visits: (a) upon initial placement of the first stent (Visit 1), and (b) at all three visits in which the subject has a stent placed for 30 days (Visits 2, 3 and 4).

The primary effectiveness endpoint will be marked as a failure for a subject if any of the following occur:

- PVR of >150 ml at any visit (Visits 1, 2, 3, and 4)
- The subject withdraws from the trial

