4.2.1. Primary Effectiveness Endpoint

PVR levels will be monitored throughout the 90 days of stent use to confirm that the patient is able to successfully empty his bladder. PVR levels are assessed on Visits 1, 2, 3 and 4 while stent is in place using abdominal ultrasound. The hypothesis is that over 90 days of stent use, 50% of the patients will be able to successfully empty their bladder, as defined by PVR of ≤ 150 ml at all four visits.

Patients where the PVR is >150 ml at 1 or more of the 4 visits will be considered a *treatment failure*. Patients who fail to attend any of the 4 scheduled visits, or withdraw prematurely, will also be treated in primary the analysis as a *treatment failure*. Patients where the PVR is <150 ml at all 4 visits will be considered a *treatment success*.

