7. ANALYSIS POPULATIONS

The following populations will be considered for the summarization and analysis of the data from this study:

Intention to Treat Population

The Intention to Treat (ITT) population includes The ITT population will consist of any enrolled patient who underwent an attempted Spanner device implant procedure. This population will be used for all of the analyses unless otherwise stated.

Per Protocol Population

The Per Protocol (PP) population will consist of all patients who are enrolled in the study, have been implanted with a Spanner device, and have completed all study visits with no major protocol deviations while enrolled in the study. A major protocol deviation is defined as any protocol deviation that may affect the primary endpoint. The PP population will only be used as an analysis population if the ITT population produces unexpected results that could have been caused by protocol deviations.

Safety Population

The safety population will consist of all subjects who are enrolled in the study.

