11.4. Medications at Screening

Data will be summarized and tabulated using descriptive statistics as described in Section 8 and the data variables as described in the SRS TLF, Table 15.

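### Use of a BPH medication that Protocol 10.2.1 prohibits does not affect primary scoring, so a man who takes one and keeps PVR at or below 150 ml counts as a stent success

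*Protocol*

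**What the plan says.** Protocol 10.2.1 allows changes in urinary-tract drugs on study ("Urinary tract medications may be continued, discontinued or initiated during the study period"), requires their use to be recorded on the eCRF, and adds that "certain urinary tract medications (anticholinergics and BPH medications) are prohibited from use during the study".

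Protocol 14.3 introduces its failure list with "The primary effectiveness endpoint will be marked as a failure for a subject if any of the following occur". The list has two items: PVR above 150 ml at any of Visits 1 to 4, and "The subject withdraws from the trial". SAP 4.2.1 begins the same way ("Patients where the PVR is >150 ml at 1 or more of the 4 visits will be considered a" treatment failure) and adds missed visits. Neither list mentions medication.

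Protocol 14.6.1 makes ITT the primary analysis set and says that the primary and secondary endpoints are analysed on both ITT and PP. SAP 7 differs: "The PP population will only be used as an analysis population if the ITT population produces unexpected results" that protocol deviations could have caused. Both documents define a major deviation as one that may affect the primary endpoint.

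The only medication table named in the SAP text is for screening (SAP 11.4: "Data will be summarized and tabulated using descriptive statistics as described in Section 8"). SAP 3.2 refers to separate table and listing templates for the full set of outputs, and SAP 8 promises that all study data will appear in a listing.

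**The concern.** The trial is single-arm and tests the success proportion against a fixed 50%. With no control arm, anything besides the stent that keeps PVR at or below 150 ml raises the observed proportion and is credited to the device. The proposed indication is for men who are not candidates for pharmacologic treatment of the prostate, so a success that depended on a BPH drug does not support the claim being sought.

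The protocol treats these drugs as incompatible with the study, but nothing carries that prohibition into the endpoint. If a man takes one, neither document says whether he is a success, a failure or not evaluable. By default he is a success. Deciding this after the data are seen would be adjudication by outcome, and the pass threshold is narrow enough for one man to matter.

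**Working it through.** **1. The plan's own figures.** Inputs: null 50%, assumed success 65%, 80% power, two-sided 5% (SAP 5.3; the Protocol 14.6.3 test is one-sided 0.025). The normal approximation gives

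n = [(1.960 × √(0.5 × 0.5) + 0.842 × √(0.65 × 0.35)) / 0.15]² = 84.8, so 85 completers, as stated.

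At n=85 the same approximation gives 80.1% power (two-sided 5%) and 88.0% (one-sided 5%), matching the SAP. The exact binomial test that both documents name gives 73.6% (53 successes needed) and 86.0% (51 needed). That is a separate matter and does not affect this point. The stated total is 105.

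**2. Following one man through the rules.** He takes a BPH drug between Visit 1 and Visit 2, and PVR is at or below 150 ml at Visits 1 to 4.

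| Rule | Result |
|---|---|
| Protocol 14.3 | No PVR above 150 ml, no withdrawal: success |
| SAP 4.2.1 | As above, no missed visit: success |
| ITT (Protocol 14.6.1, SAP 7) | Stent placement attempted: included as a success |
| PP | Excluded if the deviation is judged major; never counted as a failure |
| Deviation outputs (SAP 10, 15.5, 15.6) | Listed and tabulated; scoring unchanged |

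**3. When a drug can matter.** A PVR above 150 ml at a scheduled visit is a failure that nothing later reverses. A drug can change the score only for a man who has passed every scheduled PVR so far, takes the drug before a visit he would otherwise have failed, and passes because of it.

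**4. Pass thresholds.** With N=105 and withdrawals scored as failures, P(X ≥ r) under Binomial(105, 0.5) is:

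- r=64: 0.0157; r=63: 0.0252. At one-sided 0.025, 64 are needed (Protocol 14.6.3).
- r=62: 0.0392; r=61: 0.0590. Under the one-sided 95% lower bound, taken as exact, 62 are needed (SAP 4.1 and 13.2).

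Each man moves the estimate by 1/105 = 0.95 percentage points.

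**5. Illustration.** Neither document gives a rate of drug use or of drug-dependent success, so the share d is assumed. Put true stent-only success at 50%, and let a further share d reach PVR at or below 150 ml only because of the drug. The chance of passing is P(X ≥ r | 105, 0.50 + d):

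| d | Men (105 × d) | 64 needed | 62 needed |
|---|---|---|---|
| 0 | 0 | 1.6% | 3.9% |
| 2% | 2.1 | 4.1% | 8.9% |
| 3% | 3.2 | 6.2% | 12.6% |
| 5% | 5.3 | 12.9% | 23.2% |

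Here d is the share converted from failure to success, not the share who took a drug; the latter would be at least as large.

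**The case against.** The plan already limits the problem. BPH drugs are prohibited, entry requires men who are not candidates for pharmacologic treatment, and Protocol 17 bars deviations without prior approval except in an emergency and has all of them recorded. A deviation that may affect the primary endpoint removes the man from PP, and deviations are tabulated. Scoring observed PVR whatever other drugs are taken is also a recognised treatment-policy choice, so a failure item is one option among several. All of this is fair, and it makes frequent use unlikely. But these safeguards report or exclude such a man; none changes his ITT score. Nor does the plan say that it has chosen a treatment-policy approach, which would fit poorly with an indication for men without a drug option.

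Three stronger readings are tempting, and the documents do not support them:

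- **A drug rescues men who are failing.** A reader might infer this from the freedom to start drugs on study. Step 3 of the working rules it out once a scheduled PVR has exceeded 150 ml. For retention between visits, Protocol 21.5.6 directs device removal.
- **Permitted urinary-tract drugs inflate success.** No permitted drug that aids emptying is identified, so neither an effect nor its direction can be asserted for that group.
- **On-study medication goes unreported.** The SAP text names only a screening table, but the templates are not available here and may contain an on-study one. SAP 8 in any case promises listings of all data.

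**Conclusion.** The gap is real but narrow: prohibited BPH-drug use has no consequence in the primary ITT scoring. PP is no remedy, because it would exclude rather than fail the man, and Protocol 14.6.1 and SAP 7 disagree on whether it is run.

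Any bias from drug-dependent success is upward, and its size cannot be derived from the documents. The illustrative probabilities rest on three assumptions: stent-only success exactly at the null, N=105 with every man scored, and conversion shares of 2% to 5% chosen only to show sensitivity. On those assumptions, about two converted men take the false-pass chance above the nominal level under either decision rule. If no one takes such a drug, the effect is nil. This is an inexpensive improvement that should be made, not a flaw that invalidates the design.

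**What to change.** 1. In Protocol 14.3 and SAP 4.2.1, add a failure item: use of a BPH medication prohibited by 10.2.1 between stent placement and the last PVR (Visit 4). Apply the same item in SAP 4.2.2, through Visit 2 for the two 30-day endpoints and through Visit 4 for the 250 ml 90-day endpoint. Fix the list of drugs that count before the data are reviewed, because the documents do not define the class.
2. In SAP 13.2, add one sensitivity analysis scoring as failure any man who started another urinary-tract medication, other than an antibiotic, after Visit 1. Present it as a conservative bound, since the documents do not show that such drugs aid emptying.
3. Add a summary of on-study urinary-tract medications if the templates lack one. Attachment E lists no separate medication form, so confirm that drug name and start date are captured.
4. Reconcile Protocol 14.6.1 and SAP 7 on when PP is run.

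Cost: the data are already required on the eCRF, so the work is wording, one extra analysis and possibly one table. The success rate may fall slightly. For example, if the assumed 65% included 2% of men rescored as failures, exact power at N=105 and one-sided 0.025 would be 70.6% instead of 83.5%. Changing the primary failure definition may also need an FDA supplement under Protocol Section 16. Which drugs sites may use does not change.

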10.2.2 Use of Antibiotic Coverage

Men participating in the study will receive antibiotic coverage throughout the study, based on the investigator's antibiotic of choice after reviewing the scheduled urine cultures. Record the use of these medications on the eCRF system.

10.2.3 Additional Medical Care

Additional medical care in the form of medical office visits or home health care may be continued, discontinued or initiated during the study period. Record all medical care on the eCRF system.

10.3 Number of Investigational Devices Needed

The total sample size of n=105 subjects will be required for the study. Each subject is scheduled to receive three consecutive Spanner stents. Therefore, the estimated number of Spanners required for this study is 315.

Each subject will be measured once using the Surveyor Urethral Measurement Device to confirm Spanner size. The estimated number Surveyors used in the study is 105.

11 SUBJECTS

11.1 Inclusion Criteria

- Age > 45 years;
- In urinary retention and catheterized (indwelling or intermittent) for less than 180 days;
- Documented diagnostic history (within 180 days of study) of detrusor contractility (≥ 15 cmH₂O) confirmed via pressure-flow test;
- Negative Urinalysis on Visit 1;
- Not a candidate for pharmacologic, minimally invasive or surgical treatment of the prostate;
- Charlson Weighted Index of Comorbidity Score ≥ 1 (see **Attachment C**);
- Willing and able to sign the Informed Consent Form
- Willing and able to complete the follow-up protocol requirements;
- Experiencing catheter-induced discomfort.

11.2 Exclusion Criteria

- Current use of a urinary catheter daily for greater than 180 consecutive days immediately preceding entering into the study;
- Positive Urinalysis on Visit 1;
- Current or recent (within the last 6 months) urinary tract disease including urethral stricture, bladder stones, and other significant urological conditions or surgery;
- Surgery altering the normal uro-genital anatomy or abnormal urethral anatomy that affect the function of the lower urinary tract;
- History of conditions associated with neurogenic bladder, including spinal cord injury, multiple sclerosis, or Parkinson's disease;

CONFIDENTIAL

- Use of anticholinergic medication;
- Gross hematuria when catheter is removed on Visit 1;
- Known or suspected prostate cancer;
- Prior pelvic irradiation therapy;
- Prostatic urethral length < 4 cm or > 9 cm (combined length from the top proximal side of the bladder neck to the bottom distal side of the external sphincter)
- Intravesical enlargement of the median lobe of the prostate.
- Prior penile prosthesis

11.3 Subject Withdrawal or Discontinuation

Premature withdrawal of a subject from the study for any reason must be documented using the Study Completion eCRF. Where possible, a final evaluation should be carried out including all of the evaluations specified for Visit 4.

If a subject is withdrawn due to an Adverse Event, the final visit should be completed 1 week after resolution of the Adverse Event. If a subject is unable or unwilling to complete all of the required evaluations, obtain as many as possible. In addition, if the withdrawal is associated with an Adverse Event, follow the procedures described in Section 21.

Use the Unscheduled Visit eCRF to record the results of the evaluation.

[figure not shown]
11.4 Point of Enrollment

Each study candidate to be evaluated during screening will be asked to sign an Informed Consent Form (ICF) prior to the conduct of study specific procedures. The ICF outlines the study procedures, investigational nature of the study, protocol responsibilities, and the expected risks vs. benefits of participation.

Screening is planned to be conducted entirely at Visit 1. Subjects who meet the inclusion and exclusion criteria are enrolled in the study. Device insertion is also planned to be conducted at Visit 1.

The Investigator will retain a Screening Log of those who are considered candidates for enrollment. If a subject later declines or is excluded from enrollment, the Investigator will note the reason for non-participation in the log. Potential subjects will be identified in the log by their initials only.

Figure 9. Flowchart of Subject Screening, Enrollment and Spanner Insertion

